5.8. Analysis of Safety Data

The analysis of safety and tolerability will be performed on the SAF, as defined in Section [3.2](#).

The safety analysis will be based on the reported AEs and other safety information (nerve conduction measures, clinical laboratory evaluations, vital signs and 12-lead ECG).

Thresholds for Potential Clinically Significant Values (PCSV) in laboratory variables, vital signs and ECG are defined in Section [10.3](#).

The summary of safety results will be presented for each treatment group and by visit where applicable.

Day 1 is the first day of study drug, Day -1 is the day before Day 1, and there is no Day 0.

The time interval to detect any AEs, including AESIs (except JR identified at the 64-week telephone follow-up), or abnormalities is between the first dose of study drug dose up to the end of the Follow-Up Period (i.e., week 36/Early Termination). Any study drug-related SAEs occurring between the end of Follow-Up clinic visit and the EOS will also be included. Data collected outside this interval will be excluded from the descriptive statistics and identification of abnormalities for laboratory evaluations, ECGs and vital signs. All post-baseline data during the interval will be used in the PCSV analysis including scheduled and unscheduled assessments.

5.8.1. Primary Safety Analysis

The variables for the evaluation of peripheral nerve function are the change from baseline to week 16 (based on central reader assessment) in the amplitude and velocity from the 3 individual nerve conduction tests.

The nerve conduction variables will be analyzed using an MMRM approach based on the safety analysis set. The model will include baseline value, randomization strata, treatment, visit, and treatment-by-visit interaction. The least-squares mean estimates for the mean change from baseline to week 16, as well as the differences of the estimates between fasinumab and placebo, with their corresponding standard errors and associated 95% confidence intervals, will be provided descriptively.

No imputation will be made for Nerve Conduction values that were missing as a result of technical error, were not performed, or performed outside of scheduled visit windows. For measurements recorded as physiologically absent ("No Response", meaning outside detection sensitivity of the test), nonzero values were imputed using the 1st percentile of all non-missing values across all visits, all patients, and all treatment groups. This will be done to impute the low end of the range of detectable values while avoiding undue influence by outliers.

Data collected after discontinuing treatment up to week 16 will be included and used in the primary safety analysis. Any unscheduled repeated NCT tests data outside the window described in Section 6.6 will not be used in the primary safety analysis, but used in a sensitivity analysis.

Sensitivity Analysis

Sensitivity analyses will be performed to assess the robustness of the results generated for the primary safety variables.

Sensitivity analysis for the primary safety endpoints will be performed using similar analysis method as the primary safety analysis. For the unscheduled repeated tests at week 8, week 16 and week 36, the window described in Section 6.6 won't be used. Alternatively, the last test value prior to the next scheduled visits will be used in this sensitivity analysis. Missing nerve

conduction variables up to week 16 will be imputed using the same approach used in the primary analysis.

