7.3.2.1. Reasons for Permanent Discontinuation of Study Drug

Study drug dosing will be permanently stopped in the event of:

- A patient developing clinically significant peripheral sensory or motor neurologic events confirmed by a neurologist's examination and graded by the neurologist as at least moderate peripheral neuropathy limiting activities of daily living, ie, grade ≥2 according to Common Terminology Criteria for Adverse Events (CTCAE) v.4; study sites should use CTCAE v.4 criteria throughout the study for consistency
- Evidence of pregnancy

- A patient developing signs and symptoms indicative of carpal tunnel syndrome
- Continued noncompliance with protocol-defined maximum acetaminophen/ paracetamol use (with a maximum daily dose of 2500 mg [countries where 500 mg strength tablets/capsules are available] or 2600 mg [countries where 325 mg strength tablets/capsules are available]) during the treatment and follow-up periods, after appropriate counseling
- Continued noncompliance with the protocol, including usage of NSAIDs or other medications or non-pharmacologic treatments that are not permitted in the study, after appropriate counseling
- JR surgery
- AESI:
 - Adjudicated arthropathy, as described in Section 9.6.1.1.
 - Sympathetic nervous system dysfunction, as described in Section 9.6.1.2.
- Per protocol repeated nerve conduction test that confirms results are not within the established parameters for peroneal, sural, or ulnar nerves, as per central reader assessment and the neurologist's evaluation that confirms the diagnosis of peripheral neuropathy.
- Hepatotoxicity. Study drug should be discontinued if the following are observed:
 - 1. Total bilirubin (TBL) >2x ULN or international normalized ratio (INR) >1.5, and
 - 2. ALT or AST >3x ULN, and
 - 3. No other cause for 1 and 2 is readily apparent

Other causes of ALT, AST, and TBL elevations may include alcoholic hepatitis, autoimmune hepatitis, non-alcoholic hepatitis, heritable diseases (Gilbert's Syndrome), heart failure, and viral hepatitis.

NOTE: Study drug may be withheld in patients who do not meet criteria for permanently discontinuing study drug, until an alternative cause for drug-induced liver injury can be determined. The patient may be re-challenged if an alternative cause for elevated liver function tests is found and the liver function tests return to baseline, but only after discussion with the sponsor.

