2.2. Sample Size and Power Considerations

Approximately 180 patients will be randomized in a 1:1 ratio to fasinumab 1 mg Q4W or placebo. With this sample size, the precision of the estimated treatment difference between fasinumab and placebo at week 16 in nerve conduction velocity is no more than 1.21 m/s with a 95% confidence level, assuming a standard deviation (SD) of 3.6 m/s. This sample size provides similar precision for the estimated treatment difference in nerve conduction amplitude assuming

a SD of 3.6 μ V. Assuming a 2-sided alpha level of 0.05 and a 15% dropout rate up to week 16, an enrollment of 90 patients per group will provide at least 80% power to detect an effect size of 0.46 in the Western Ontario and McMaster Universities Osteoarthritis Index (WOMAC) pain and physical function subscale scores (ie, absolute treatment difference of 1.1 between fasinumab and placebo with an SD of 2.4). The assumed treatment difference and SD are based on results from study R475-PN-1227.

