5.7. Analysis of Efficacy Data

5.7.1. Efficacy Analysis

The secondary efficacy endpoints of the study are:

- Change from baseline to week 16 in WOMAC pain subscale score
- Change from baseline to week 16 in WOMAC physical function subscale score

The following hypotheses will be tested:

- $H_{0,1}$: There is no treatment difference between fasinumab 1 mg Q4W and placebo in WOMAC pain subscale at week 16
- $H_{0,2}$: There is no treatment difference between fasinumab 1 mg Q4W and placebo in WOMAC physical function subscale at week 16

For the above hypotheses, the estimand is the difference in means between each fasinumab 1 mg Q4W and placebo in the change from baseline to week 16 in the WOMAC pain and physical function scores in the FAS, regardless of whether or not prohibited medication had been taken. Any data collected after discontinuing treatment will not be used in the main efficacy analysis, but used in a treatment policy sensitivity analysis.

Each of the secondary efficacy variables will be analyzed using a multiple imputation approach with mixed-effect model for repeated measure (MMRM) based on the FAS. For patients who permanently discontinued treatment due to lack of efficacy, death or AEs, their missing WOMAC subscale scores after discontinuation will be imputed with values centered at the mean baseline WOMAC subscale score of the treatment group that patient was randomized to. For patients who discontinued treatment due to other reasons, their missing WOMAC subscale scores after discontinuation will be imputed under missing-at-random assumption using the regression method with adjustment for covariates including treatment group, randomization strata (K-L category [2 to 3, or 4] and index joint [knee, hip]) and baseline WOMAC subscale score. Intermittently missing WOMAC subscale prior to treatment discontinuation will be imputed using Markov Chain Monte Carlo method.

Missing data up to week 16 will be imputed 50 times to generate 50 complete data sets by using the SAS procedure PROC MI following the 3 steps below:

- Step 1: The monotone missing pattern is induced by Markov Chain Monte Carlo (MCMC) method in MI procedure using seed number 4751758.

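### No planned analysis tests the missing-at-random assumption for patients with no week-16 nerve test, and for the six primary safety endpoints that assumption leans toward no harm

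*SAP*

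**What the plan says.** The primary endpoints are changes from baseline to week 16 in velocity and amplitude for the peroneal, sural and ulnar nerves (SAP 4.6.1). After baseline, nerve tests are scheduled at weeks 8, 16 and 36.

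SAP 5.8.1 fits an MMRM on the safety analysis set with baseline, strata, treatment, visit and treatment-by-visit terms. On gaps in the data it says: "No imputation will be made for Nerve Conduction values that were missing as a result of technical error, were not performed". Tests done outside the scheduled windows are treated the same way. The only imputation is for physiologically absent responses, which receive the 1st percentile of all observed values. Tests taken after stopping drug, up to week 16, enter the primary analysis.

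The single specified sensitivity analysis drops the Section 6.6 window for unscheduled repeats and takes the last value before the next scheduled visit. On missing data it says that nerve "conduction variables up to week 16 will be imputed using the same approach used in the primary analysis".

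Protocol 10.4.4.1 mentions two optional extras: an analysis of observed data without imputation, and one that includes off-treatment data. The second is already the SAP's primary analysis.

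On size, SAP 2.2 says that the precision for velocity "is no more than 1.21 m/s with a 95% confidence level, assuming a standard deviation (SD) of 3.6 m/s". The dropout assumption ("Assuming a 2-sided alpha level of 0.05 and a 15% dropout rate up to week 16") is stated for the WOMAC power, not for the nerve precision.

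**The concern.** An MMRM without imputation assumes that missing values can be predicted from the patient's own observed values and from the pattern in that patient's arm. A patient with a week-8 value, or a usable early-termination value, is predicted from that value plus the arm's course. A patient with no post-baseline test contributes nothing to the estimate.

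For a benefit endpoint this is a common starting point. For a harm endpoint it is the less cautious assumption: if fasinumab patients who leave are losing nerve function faster than the model predicts, the week-16 difference moves toward no effect. The protocol gives some reason to ask. It stops study drug for "A patient developing clinically significant peripheral sensory or motor neurologic events confirmed by a neurologist's examination" and for neuropathy confirmed after an abnormal repeat nerve test (7.3.2.1), and a patient who stops drug may also choose to withdraw (7.3.2).

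No formal test is planned for the nerve measures (Protocol 10.1), so the LS mean difference and its confidence interval are the primary result. The analysis offered as evidence of robustness shares the primary analysis's missing-data assumption, so it would agree with the primary result whether or not that assumption held.

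**Working it through.** **The plan's own figure.** Inputs from SAP 2.2: 90 per arm, SD 3.6 m/s. The half-width is t(0.975, 2n-2) x 3.6 x sqrt(2/n).

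- n = 90: 1.06 m/s.
- n = 76 (90 x 0.85 = 76.5, rounded down): 1.15 m/s.
- n = 76 with a factor for 80% assurance on the interval width: 1.208 m/s, which matches 1.21. The assurance factor is inferred; the plan does not state it.

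All three satisfy the stated upper limit, so 1.21 m/s is used as the yardstick.

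**Size of the hidden part.** Suppose a share p of the fasinumab arm has no week-16 test and an extra loss d at week 16, and placebo dropouts have no extra loss. Let q be the share of the arm that is affected and has a week-8 value, u the share with no post-baseline test, f the fraction of the loss already present at week 8, and r the week-8/week-16 correlation, with equal SDs at both visits. The model's week-16 mean equals the completers' week-16 mean, plus r times the gap between the week-8 mean of everyone tested and that of the completers. Baseline and strata terms are left out.

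- True shift = p x d
- Shift recovered by the model = r x f x d x q / (1 - u)
- Hidden part = true shift - recovered shift

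The documents give none of d, f, q, u or r. Assume d = 2 m/s and r = 0.6.

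| Scenario | True shift | Recovered | Hidden | Hidden / 1.21 |
|---|---|---|---|---|
| p = 15%, half with a week-8 value (q = u = 7.5%), f = 0.5 | 0.15 x 2 = 0.30 | 0.6 x 1 x 0.075/0.925 = 0.049 | 0.25 | about 20% |
| p = 5%, half with a week-8 value (q = u = 2.5%), f = 0.5 | 0.05 x 2 = 0.10 | 0.6 x 1 x 0.025/0.975 = 0.015 | 0.085 | 7% |
| p = 5%, all with a week-8 value (q = 5%, u = 0), f = 1 | 0.10 | 0.6 x 2 x 0.05 = 0.06 | 0.04 | 3% |

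A simulation of the first row gave a true difference of -0.302 and an estimate of -0.051, in agreement.

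**How far the hidden fraction moves.** A second simulation used 90 per arm, 15% dropout and 3.6 m/s (1 SD) extra loss in every fasinumab dropout. It varied r over 0.3, 0.5 and 0.7, the share of dropouts with a week-8 value over 0, 0.5 and 1, and f over 0.5 and 1. The true difference was about -0.56 m/s.

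- No dropout with a post-baseline test: about 100% hidden.
- Half of dropouts with a week-8 value: 61 to 93% hidden.
- All dropouts with a week-8 value: 66 to 84% hidden if f = 0.5, and 30 to 69% if f = 1.

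**An upper check.** A true shift equal to 1.21 m/s needs an average extra loss of 1.21/0.15 = 8.07 m/s, or 2.24 SD, across the whole 15%.

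**The case against.** The strongest reply is that stopping drug is not the same as missing data. Patients who stop are encouraged to stay and asked to attend all remaining visits (Protocol 7.3.2 and 8.1.3), and SAP 5.8.1 uses their tests. Those stopped because of an abnormal repeat nerve test have had that loss recorded. Patients who withdraw should have a nerve test at early termination if more than two weeks have passed since the last one. Nothing in the documents shows that patients with neuropathy tend to withdraw, and Protocol Section 1 reports few discontinuations for adverse events in the fasinumab program.

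Most of this stands. It narrows the affected group to study withdrawals and missed tests, and makes 15% with uniform extra loss close to a worst case. It does not remove the assumption for those who remain untested. The early-termination safeguard is also uncertain: the windows in SAP 6.6 name only unscheduled tests, while SAP 6.5 maps early-termination visits on days 72 to 99 to week 12, where no nerve test is scheduled.

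A reader might also infer inconsistent caution from the WOMAC rule: "For patients who permanently discontinued treatment due to lack of efficacy, death or AEs, their missing WOMAC subscale scores after discontinuation will be imputed" around the baseline mean. The contrast is weak. The main WOMAC analysis discards off-treatment data and so needs a rule for those patients, whereas the nerve analysis keeps such data. Centring nerve values at baseline would mean assuming no harm.

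**Conclusion.** The point holds in a limited form. For the six primary endpoints, neither the SAP nor the protocol's optional extras depart from missing at random, and the assumption leans toward no harm if fasinumab patients without a week-16 test do worse than predicted. At 2 m/s extra loss the hidden part runs from about 0.04 m/s to about 0.25 m/s, depending mainly on whether 5% or 15% of the arm is affected. It rests on an assumed correlation of 0.6, on harm in fasinumab dropouts only, and on how much of the loss an earlier test captured.

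Two stronger readings are not supported. One is that every patient without a week-16 test is given the course of those who stayed. The model uses a patient's own week-8 or usable early-termination value, and the comparison group includes off-drug patients who kept attending. The other is that the trial as a whole would hide nerve harm. The point concerns the primary LS mean difference only; adverse events leading to withdrawal, peripheral sensory events of special interest and neurological examinations are reported separately and could show it.

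The change should be made, but the hidden part in these scenarios stays well inside the stated precision.

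**What to change.** In SAP 5.8.1:

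1. Add one delta-adjusted sensitivity analysis. Multiply impute missing week-16 nerve values (50 data sets, as in 5.7.1), then shift the imputed values downward in fixed steps for fasinumab patients with no week-16 test. Do this once for all of them, and once only for those who stopped or withdrew for an adverse event, nerve finding or death. Vary the placebo shift as well. Let the steps run up to a 12% fall from baseline. That figure appears in Protocol 9.6.1.3 and serves here purely as an analysis bound. Report the LS mean difference and 95% CI at each step.
2. Report by arm the number of safety-set patients with no week-16 test and with no post-baseline test.
3. Keep the sentence saying that missing values are handled as in the primary analysis, but state that it refers to the 1st-percentile rule for No Response values. Deleting it would remove that rule from the sensitivity analysis.

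The cost is SAP wording and one more table from data already collected, with no new visits or patients. The downside is that less favourable estimates may appear beside the primary result. If few tests are missing, the counts will show that the issue is small.

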5.8.2. Adverse Events

All AEs reported in this study will be coded using the currently available version of MedDRA[®]. Coding will be to lowest level terms. The verbatim text, PT, and SOC will be listed.

- *Pre-Treatment Adverse Events* are defined as AEs that developed or worsened during the pre-treatment period.
- *Treatment-Emergent Adverse Events (TEAE)* are defined as AEs that developed or worsened during the On-Treatment Period.
- *Post-Treatment Adverse Events* are defined as AEs that developed or worsened more than 28 days after the last dose of study drug.

Post treatment AEs and all AEs during the study will be summarized similarly as TEAEs.

Summaries of TEAEs by treatment group will include:

- Overview of TEAEs, summarizing number of events, summarizing number and percentage of patients within the specified category
 - Total number of TEAEs
 - Total number of Serious TEAEs
 - Total number of AESIs
 - Patients with any TEAEs
 - Patients with any Serious TEAEs
 - Patients with any AESIs
 - Patients with any TEAEs leading to death
 - Patients with any TEAEs leading to withdrawal from study
 - Patients with any TEAEs leading to permanent study treatment discontinuation
- TEAEs by SOC and PT
 - All TEAEs

- TEAEs by severity: mild, moderate or severe
- TEAEs resulting in permanent study treatment discontinuation
- Treatment-related TEAEs by SOC and PT
 - All treatment-related TEAEs
- TEAEs by PT
 - All TEAEs
 - TEAEs resulting in permanent study treatment discontinuation
- Post-treatment AEs by SOC and PT
 - All post-treatment AEs
 - Post-treatment AEs by severity: mild, moderate or severe
- Serious TEAEs by SOC and PT
- Post-treatment Serious AEs by SOC and PT
- All serious AEs on study by SOC and PT
- Non-serious TEAEs by SOC and PT
- Post-treatment non-serious AEs by SOC and PT
- All non-serious AEs on study by SOC and PT
- All AEs on study by SOC and PT
 - All AEs
 - All AEs by severity: mild, moderate or severe
- Death

Counts will be provided according to treatment group for each PT within each SOC. Percentages will be calculated using the number of patients in each treatment group using the respective SAF.

Primary SOC's will be sorted by decreasing frequency in the fasinumab group. Within each primary SOC, PT's will be sorted by decreasing frequency in the fasinumab group. For tables presenting severity of events, the worst severity will be chosen for patients with multiple instances of the same event.

A second type of table with counts of each primary SOC in decreasing order of frequency will be provided. A third type of table with counts of each PT in decreasing order of frequency will also be provided.

The following listings will be included:

- AEs leading to death
- TEAEs leading to permanent discontinuation from study drug (not applicable to post-treatment AEs)
- TEAEs leading to withdrawal from study
- Patients with Serious TEAEs
- AESIs
- Deaths
- All Joint Replacements
- All AEs
-

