7.3.2.2. Reasons for Temporary Discontinuation of Study Drug

Study drug may be temporarily discontinued due to medical need, as determined by the investigator. Study drug will be temporarily withheld while awaiting imaging adjudication for worsening joint pain or when routine imaging suggests AA and prompts the need for additional imaging (see Section 9.6.1.1), for patients who are determined to have orthostatic hypotension or determined to have new or worsening symptoms suggestive of SNS dysfunction while awaiting evaluation by a specialist (see Section 9.6.1.2), or for patients with symptoms of peripheral neuropathy while awaiting evaluation by a specialist and/or results of a nerve conduction test (see Section 9.6.1.3).

Study drug should not be re-started until the next study visit, unless imaging, nerve conduction test results, or neurology evaluation results are available within the current visit window and confirm that study drug may be restarted.

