9.6.1.3. Peripheral Sensory Adverse Events

Altered peripheral sensation (eg, paraesthesia and hypoaesthesia) is an important identified risk with fasinumab (see Investigator's Brochure) and other anti-NGF compounds. Any peripheral sensory AE that, per the investigator's judgment, requires a neurology or other specialty consultation must be reported as an AESI. If any peripheral sensory event persists for 2 months, the patient must be referred for a neurology or other specialty consultation and the event must be reported as an AESI. Refer to the study manual for further details related to reporting of peripheral sensory neuropathy AEs.

If the repeated per-protocol nerve conduction test performed on the regions of the peroneal, sural, or ulnar nerves at any post-baseline visit shows a difference from baseline of >12% (based on central reader assessment), the patient will be referred for a neurology evaluation. If the neurologist's evaluation confirms the diagnosis of peripheral neuropathy, the study drug will be permanently discontinued. Refer to the study manual for further details related to reporting of results of nerve conduction tests.

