5. STATISTICAL METHODS

For continuous variables, descriptive statistics will include the following information: the number of patients reflected in the calculation (n), mean, median, SD, minimum, 1st & 3rd quartiles (Q1 & Q3), and maximum.

For categorical or ordinal data, frequencies and percentages will be displayed for each category.

Period of Observation - Unless otherwise stated, analysis of all safety and non-safety variables captured at multiple visits will be analyzed by the following observation periods:

- The *Pre-Treatment Period* is defined as the time from signing the ICF to before the first dose of study drug.
- The *On-Treatment Period* is defined as the time from the first dose of study drug up to 28 days after the last dose of study drug.
- The *Follow-Up/Post-Treatment Period* is defined from the end of the On-Treatment Period to the date of the follow-up clinic visit (Week 36 visit) or early termination date.

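### Outputs of AEs that stop study drug or end participation are limited to TEAEs, so some such AEs can be classed as post-treatment and left out

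*SAP*

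**What the plan says.** **Window.** SAP section 5 defines the On-Treatment Period as "the time from the first dose of study drug up to 28 days after the last dose of study drug". Under SAP 5.8.2, TEAEs "are defined as AEs that developed or worsened during the On-Treatment Period", and post-treatment AEs are "AEs that developed or worsened more than 28 days after the last dose of study drug".

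**Outputs.** SAP 5.8.2 plans an overview row, "Patients with any TEAEs leading to permanent study treatment discontinuation", with matching tables by SOC and PT and by PT. The listing is "TEAEs leading to permanent discontinuation from study drug (not applicable to post-treatment AEs"). AEs leading to withdrawal from the study have one overview row and one listing, both for TEAEs.

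**Dosing and holds.** Protocol 7.1 allows ±7 days around each scheduled dose. A dose whose window is missed is skipped, and dosing resumes at the next scheduled date. Protocol 7.3.2.2 provides for holds, for example "Study drug will be temporarily withheld while awaiting imaging adjudication for worsening joint pain or when routine imaging suggests AA", and also for orthostatic hypotension, suspected SNS dysfunction and symptoms of neuropathy. A permanent stop can follow evaluation. For nerve findings, Protocol 9.6.1.3 says "If the neurologist's evaluation confirms the diagnosis of peripheral neuropathy, the study drug will be permanently discontinued".

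**The concern.** The listing note assumes that a post-treatment AE cannot be the reason study drug is stopped. On a four-weekly schedule with a 28-day tail, the TEAE window closes at about the visit when the next dose is due. If that dose is held or skipped and dosing never resumes, the patient is post-treatment under the SAP's definition before anyone has decided to stop. An AE starting in that gap can cause the permanent stop and still be filtered out.

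AEs leading to discontinuation are a standard by-arm tolerability comparison. Holds are used for suspected joint, sympathetic and peripheral nerve events, which are the AEs this program monitors most closely. The disposition table in SAP 5.5.2 counts all treatment stops by reason without a TEAE limit. The two outputs may therefore disagree, and the AE output may not show which events stopped treatment.

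**Working it through.** **Inputs.** Doses fall on study days 1, 29, 57 and 85, end of treatment is day 113 and week 36 is day 253 (schedule of events). The dose and visit window is ±7 days after day 1 (Protocol 7.1 and schedule). The TEAE tail is 28 days (SAP section 5).

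**1. The plan's own figure.** Window end = day of last dose + 28. With all four doses, 85 + 28 = 113, which is the stated week 16 day.

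**2. A held dose that is never restarted.** If the dose due on day 29, 57 or 85 is held, the last dose is day 1, 29 or 57. The window then ends on 1 + 28 = 29, 29 + 28 = 57 or 57 + 28 = 85. On the nominal schedule that is the hold visit itself.

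**3. A sign first found at the hold visit (for example orthostatic hypotension).** On the nominal schedule it falls on the last day of the window and is a TEAE. With offsets *a* for the last dose and *b* for the hold visit, each from −7 to +7, the gap is 28 + *b* − *a*. This ranges from 14 to 42 days, or 21 to 35 after the fixed day-1 dose. The sign is post-treatment when *b* > *a*: (225 − 15)/2 = 105 of 225 pairs, or 46.7%. After the day-1 dose it is 7 of 15 offsets, also 46.7%. This is a share of equally weighted visit offsets, given onset exactly at that visit. It is not a share of events.

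**4. A new AE during a hold or skip.** Suppose the last dose is day 29 and the day-57 dose is skipped. The window closes on day 57 and the next dose is due on day 85. If an AE starting on days 58 to 85 means that dosing never resumes, it is post-treatment by definition. That gap is 85 − 57 = 28 days. No assumption about dating is needed.

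**5. An event dated at confirmation.** Neither document gives an onset-date rule for adjudicated arthropathy, SNS dysfunction or neuropathy. If sites used the confirmation date, an event would be left out when 28 + *b* − *a* + delay > 28. Over the 225 pairs:

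| Assumed delay | Pairs left out |
|---|---|
| 1 day | 120/225 = 53% |
| 10 days | 210/225 = 93% |
| 28 days | 225/225 = 100% |

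**6. An event dated from earlier symptoms.** Protocol 9.6.1.1 normally requires worsening joint pain to last at least 2 weeks. With no skipped dose the latest onset is 42 − 14 = 28 days after the last dose, so it is always a TEAE.

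**7. Withdrawal from the study.** Follow-up time to week 36 outside the TEAE window is 253 − (last dose + 28):

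| Last dose (day) | Days outside the window |
|---|---|
| 1 | 224 |
| 29 | 196 |
| 57 | 168 |
| 85 | 140 |

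An AE starting in that time and leading to withdrawal is outside the TEAE-only row and listing. No hold or dating assumption is involved.

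**The case against.** The strongest reply is that TEAE status depends on when an event developed or worsened, not on when it was confirmed or when drug was stopped. A reader might infer that events passing through the hold, confirm and stop sequence are generally lost. The documents do not support that:

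- The trigger usually exists at or before the hold, and joint pain of at least 2 weeks before a hold visit, with no skipped dose, always stays a TEAE.
- Scheduled post-baseline X-rays are at weeks 16 and 36, after the last dose at week 12, so they leave no dose to hold.
- Only the week 8 nerve conduction test falls at or before a remaining dose, and on the nominal schedule it is inside the window.
- If drug is restarted, the window extends to the later last dose plus 28 days.
- Dating at confirmation is an assumption. AE recording procedures are in a study manual outside these documents.

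All of this stands and limits the size of the problem.

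It can also be said that the events appear elsewhere. They do: the post-treatment and all-AE tables, the AESI outputs, arthropathy incidence through week 36, and disposition by reason. None of these is planned as a by-arm summary of which AEs stopped treatment.

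Protocol 10.4.4.2 also refers to treatment-emergent AEs leading to discontinuation, so the SAP follows it. However, Protocol 10.4.4 ties the treatment period to the week 12 dose plus 4 weeks, and the TEAE endpoint runs through week 16. That can be read as a fixed end at day 113, which is longer than the SAP's window for patients who stop early.

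Finally, SAP 5.8.2 says in general terms that post-treatment AEs will be summarized in the same way as TEAEs. For discontinuation, the listing note rules this out. For withdrawal, the sentence could be read to cover the gap, but the itemized post-treatment tables include no withdrawal row. At best this leaves an ambiguity, while Protocol 9.4.4 requires all AEs leading to withdrawal to be reported to the sponsor.

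**Conclusion.** The point holds as a limited gap in specification. Under the SAP's definitions some AEs that cause permanent discontinuation can be post-treatment, so the parenthetical is wrong as a general statement and the outputs can be incomplete. The routes are a sign first found at a dosing visit more than 28 days after the last dose, a new AE after day 28 while a dose is held or skipped, and an event dated at later confirmation if sites date it that way. For withdrawal, AEs starting in follow-up are outside the outputs as listed, unless the general sentence is read to include them.

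The number of events affected cannot be derived from the documents. It would be wrong to read 46.7% as the share of stopping events lost: it assumes uniform visit timing and onset exactly at the visit, and the nominal-schedule figure is 0%. Nor does any safety signal vanish from the report. The loss is confined to the discontinuation and withdrawal outputs, which may not reconcile with disposition. The primary nerve conduction endpoints are not affected.

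**What to change.** In SAP 5.8.2:

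- Select AEs leading to permanent discontinuation of study drug, and AEs leading to study withdrawal, by the action-taken or outcome field, for any AE from first dose to week 36 or early termination.
- Delete the parenthetical on post-treatment AEs from the listing.
- Flag the TEAE subset in each table and listing.
- Reconcile the totals with the AE reason in the disposition table, allowing for its use of the FAS where the AE outputs use the SAF.

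It would also help to state how onset is dated for adjudicated arthropathy, SNS dysfunction and neuropathy, and to reconcile the SAP's per-patient window with the protocol's week 12 plus 4 weeks.

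The cost is a change of wording and of a filter. The planned TEAE outputs already need the same field, so no new data are required. The listing of AEs leading to death is already selected by outcome without a TEAE limit. The one downside is that the headline counts are no longer strictly TEAE counts; the flagged subset keeps those available.
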